## **SYNOPSIS**

#### **Study Description**

#### PROJECT SUMMARY/ABSTRACT

Cannabis use and availability continue to rise significantly in the US. It is critical to expand our knowledge of the negative and positive effects of cannabis to "catch up" to the current reality of widespread and growing use. Cannabis and tetrahydrocannabinol (THC), its primary psychoactive chemical, have widespread effects on neural glutamate homeostasis, and specifically metabotropic glutamate receptor 5 (mGluR5). mGluR5 regulates transmission of glutamate and plays a critical role in neural plasticity (i.e., long-term potentiation; LTP), memory, learning, mood, and addiction. Specifically, it is thought that mGluR5 activation by glutamate initiates production of endocannabinoids (i.e., 2-AG) that bind retrograde to presynaptic cannabinoid receptor 1 (CB1). This pathway inhibits further glutamate release and modulates synaptic plasticity diffusely in the brain. However, cannabis binding to CB1 disrupts this normal mechanism of glutamate homeostasis. While the relationship between cannabis use and glutamate regulation has been explored in preclinical models, it has not been well-characterized in humans, and particularly in people with cannabis use disorder (CUD). Our preliminary data have demonstrated for the first time that mGluR5 availability in the fronto-limbic circuit, as measured by [18F]FPEB and positron emission tomography (PET), is higher in current cannabis users as compared with healthy controls (HC). Our electroencephalography (EEG) data show that chronic exposure to cannabis is associated with disruptions in theta band (4-7 Hz) neural oscillations, which are important for memory processes, and dependent on intact CB1 and mGluR5 function. Furthermore, a strong correlation linking impulsivity (an important clinical feature of CUD) with mGluR5 availability was observed in people who use cannabis. We therefore propose to conduct the first in vivo human multimodal neuroimaging study exploring the relationship between mGluR5 availability (PET), neural oscillations (EEG), and cognitive function in people with CUD. The goal is to test the overall hypothesis that mGluR5 availability is higher in people with CUD compared with HC. This study will advance our understanding of cannabis effects on the neural glutamate system in humans and may lead to the development of novel therapeutics and biomarkers to treat people with CUD. In Aim 1, we will determine differences in mGluR5 availability between people with CUD and HC in the fronto-limbic brain circuit. Aim 2 examines the associations between mGluR5 availability, CUD severity, neural oscillations, and cognitive function in CUD subjects. Aim 3 will determine how prolonged abstinence from chronic cannabis use affects mGluR5 availability, neural oscillations, and cognitive function in CUD subjects. The results from this innovative multimodal imaging study will improve our understanding of how chronic cannabis use and abstinence impacts neural glutamate receptors (mGluR5), and how this neurochemical mechanism relates to neural function (EEG) and clinically relevant functional measures of CUD (i.e., disease severity and impulsivity).

#### **Objectives**

#### **SPECIFIC AIMS**

Significance and Rationale: Cannabis is an addictive drug that is now widely available. Approximately 30% of cannabis users may have cannabis use disorder (CUD), and nearly 12 million young adults used cannabis in 2019. Of note, there are currently no effective treatments for CUD. There is an urgent need to better understand the consequences, and potential underlying causes, of CUD. Glutamate is the brain's primary excitatory neurotransmitter, and is strongly implicated in addictive disorders. Preclinical research indicates that chronic cannabinoid exposure disrupts glutamate homeostasis. However, the underlying mechanisms of this effect are incompletely understood in humans. Therefore, the goal of this proposal is to advance our mechanistic understanding of the consequences of CUD, with focus on metabotropic glutamate receptor 5 (mGluR5). This proposal has the potential to develop novel therapeutic targets for individuals with CUD. mGluR5 in chronic cannabis use: mGluR5s are located mostly post-synaptically and on glia, and play a critical role in neural plasticity (i.e., long-term potentiation; LTP), memory, learning, mood, and addiction. 8,9 Using [18F]FPEB and positron emission tomography (PET) neuroimaging, we can measure mGluR5 availability in vivo in people. Cannabis is known to significantly alter the same neurobehavioral functions mediated by mGluR5. Using electroencephalography (EEG), we have the capacity to relate mGluR5 availability with neural functions underlying memory and synaptic plasticity in people in vivo. Preclinical models have revealed an intimate relationship between mGluR5 and the cannabinoid system. 11 Specifically, mGluR5s on post-synaptic neurons regulate glutamate transmission through the synthesis of (natural) endocannabinoids (i.e. 2-AG). 2-AG binds to the presynaptic cannabinoid receptor 1 (CB1), which inhibits excessive glutamate release via negative feedback. Chronic cannabis use disrupts this homeostatic process, most notably leading to reduced synaptic glutamate release from pre-synaptic terminals via alterations in CB1 function. 12-15 These *pre-synaptic* changes likely reflect compensatory mechanisms related to chronic cannabis exposure. However, no studies have examined the effect of chronic cannabis use on *post-synaptic* function in CUD. Given the central role of *post-synaptic* mGluR5 in the endocannabinoid system, it is critical to examine mGluR5 in people with CUD.

Preliminary Data, Approach, and Aims: Our preliminary data demonstrate for the first time that mGluR5 availability in the fronto-limbic circuit (orbitofrontal, anterior cingulate, ventromedial prefrontal, and dorsolateral prefrontal cortices, hippocampus, and amygdala), as measured by [18F]FPEB PET neuroimaging, is higher in current cannabis users as compared with non-users (adjacent figure). In parallel, our preliminary EEG data show that chronic exposure to cannabis is associated with disruptions in theta band (4-7 Hz) neural oscillations, which are important for memory processes, 16 and dependent on intact mGluR5 and CB1

function. Further, strong correlations linking neurocognition with mGluR5 availability were observed in cannabis users. Thus, we propose to conduct the first ever *in vivo* human multimodal neuroimaging study (PET/EEG) examining the relationships between mGluR5 availability, neural oscillations, and neurocognitive function in people with CUD. Outcome measures are focused on clinically relevant markers of CUD severity.

Aim 1: To determine differences in fronto-limbic mGluR5 availability between people with cannabis use disorder (CUD; n = 30) and healthy controls (HC; n = 30). Subjects will undergo [18F]FPEB PET neuroimaging to determine mGluR5 availability. Hypothesis 1: Fronto-limbic mGluR5 availability will be higher in individuals with CUD compared with HC.

Aim 2: Within CUD subjects, to examine the associations between mGluR5 availability and: (a) CUD severity; (b) impulsivity; (c) EEG; and (d) neurocognition. CUD severity and impulsivity will be determined by validated instruments. EEG outcomes (e.g., theta power, LTP) known to be sensitive to both cannabis and glutamate will be collected during tasks of verbal memory and neural plasticity (long term potentiation; LTP). Hypothesis 2: Higher mGluR5 availability will be associated with: (a) greater CUD severity (by DSM-5); (b) higher impulsivity; (c) lower theta-band power and LTP, and (d) worse performance on verbal memory.

Aim 3: Within CUD subjects, to determine changes in mGluR5 availability, EEG, and neurocognition following cannabis abstinence. CUD subjects from Aim 1 will repeat PET scanning, EEG, and cognitive testing following a 28-day period of confirmed abstinence aided by contingency management. Hypothesis 3: Following cannabis abstinence: (a) mGluR5 will decrease; (b) theta power/LTP will be increased; (c) memory will improve.

**Impact:** The results from this innovative multimodal imaging study will improve our understanding of how chronic cannabis use impacts glutamate homeostasis via measures of mGluR5, and how this neurochemical mechanism relates to clinically relevant measures of brain function (CUD severity, impulsivity, EEG, and cognitive function). It will advance our mechanistic understanding of cannabis addiction and may lead to the development of novel therapeutics and biomarkers for people with CUD.

#### **Endpoints**

The primary endpoint is mGluR5 availability, as measured by FPEB, in cannabis-maintained and abstinent states.

Secondary endpoints are EEG outcomes and cognitive performance.

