# 9.2 Sample Size Considerations

# STATISTICAL DESIGN AND POWER

Frequency distributions and descriptive statistics for all variables will be computed prior to conducting analyses. If Shapiro-Wilk normality tests indicate non-normality for any continuous variable, we will compute necessary data transformations (e.g., logarithmic base 10) prior to conducting analyses. Of note, to conserve power, we will compute an average  $V_T$  value across the 6 study ROIs to be used in all PET analyses. This choice is supported by the fact that preliminary data revealed large magnitude (i.e., r's>0.80-0.95) correlations between OFC, dlPFC, amygdala and hippocampus [ $^{18}$ F]FPEB  $V_T$ . Thus, we plan to treat this set of regions as a circuit and compute a mean composite score of [ $^{18}$ F]FPEB  $V_T$  for use in analyses.

Aim 1: To determine differences in fronto-limbic mGluR5 availability between people with cannabis use disorder (CUD; n = 30) and healthy controls (HC; n = 30). Hypothesis 1: Fronto-limbic mGluR5 availability will be higher in individuals with CUD compared with HC. Power Calculations for Hypothesis 1: We approached power calculations by considering both our preliminary data and relevant and reliable literature (i.e., conducted with rigorous scientific methodologies, published in competitive, peer reviewed journals, with sufficient sample sizes) to determine the magnitudes of effect sizes that we might reasonably expect to observe in this study. No studies outside of our preliminary ones presented above (Research Strategy, Section C.1.a) have examined this topic of study specifically. However, we identified studies which examined differences in receptor availability in vivo between individuals who did and did not report use of cannabis using PET. For example, a recent examination of CB1 receptor availability in cannabis users vs. non-users showed a mean VT 15% lower (d=-1.11). Another study found 20% lower CB1 in chronic daily cannabis users relative to non-users. Based on the

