information provided in each manuscript, we calculated effect sizes for group differences. Observed effect sizes for group comparisons of cannabis users vs. non-users ranged from d= -0.68 to -1.77, with a median of d=-1.11. These effect sizes are consistent with those observed in our preliminary data, which showed a large effect size associated with differences in mGluR5 availability in CB relative to healthy control individuals in the fronto-limbic circuit (d= 1.72). We will evaluate hypothesis 1 (higher mGluR5 availability in cannabis users) using univariate analysis of variance (ANOVA). Assuming  $\alpha$ =0.05 (two-tailed test) and two groups (cannabis vs. control), our proposed sample size of 60 (30 per group) will provide 81.07% statistical power to detect group differences as small as d= 0.82, which is smaller than the median effect size observed in previous literature and that observed in our preliminary data. Data Analysis for Hypothesis 1: As stated, we will conduct a univariate ANOVA to compare mean fronto-limbic [18F]FPEB  $V_T$  between the HC and cannabis groups. Groups will be carefully matched on demographic variables. However, any demographic variables that differ significantly between groups, including notably age and sex, will be considered for entry as additional fixed factors (categorical variables) or covariates (continuous variables). A significant group difference suggestive of higher mGluR5 availability in CUD subjects will be considered supportive of Hypothesis 1. We will also conduct exploratory analyses to examine betweengroup differences in mGluR5 in other regions, including those involved in affective and cognitive dysregulation (e.g., thalamus, striatum, insula), at the same significance level.

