Aim 3: Within CUD subjects, to determine changes in mGluR5 availability, EEG, and neurocognition following cannabis abstinence. Hypothesis 3: Following cannabis abstinence: (a) mGluR5 will decrease; (b) theta power/LTP will be increased; (c) memory will improve. Power Calculations for Hypothesis 3: Using the same standards applied for Aims 1 and 2, we considered our preliminary data and conducted a literature review to determine the magnitude of effect sizes we might reasonably expect to observe with respect to change in mGluR5, EEG, and cognition as a function of abstinence from cannabis. Values necessary to calculate associated effect sizes were not provided in the reviewed literature. For example, Hirvonen and colleagues (2012) observed a significant increase in CB1 receptor availability in cannabis users after abstinence in both the PFC and amygdala. While percent change (pre-post abstinence) could be roughly estimated from the figure provided, exact values are not available, preventing effect size estimation. We do not have preliminary data examining participants pre- and postcannabis abstinence. However, we believe that comparison of available PET data showing in vivo mGluR5 availability in current cannabis users compared with former users may be indicative of the magnitude of change we can expect to see following abstinence. Comparison of mGluR5 availability in current and former cannabis users in our preliminary sample (n= 5 per group) showed a large effect (d = -1.2). We will evaluate Hypothesis 3 using repeated measures ANOVA. Using a moderate effect size estimate of d = 0.58 at  $\alpha = 0.05$  (highly conservative relative to the noted relevant finding in our preliminary data), a priori power analysis suggested we will require n = 30 to achieve 80.13% power for the planned analysis. Data analysis for Hypothesis 3: To test Hypotheses 3, we will conduct 3 repeated measures ANOVAs to examine changes pre- and post-cannabis abstinence in n = 30 CUD subjects. Specifically, models will evaluate: (1) changes in mGluR5 availability; (2) changes in  $\theta$ -band power and coherence; (3) changes in cognition pre-post abstinence from cannabis in the CUD group. Variables that differ significantly between groups, including age and sex, will be considered for entry into the models. A statistically significant result indicative of lower mGluR5 availability following abstinence (model 1) or higher  $\theta$ - band power and coherence (model 2) and improved cognition (model 3) will be considered supportive of Hypothesis 3.

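### The plan names one primary endpoint but not the contrast that decides it: two tests of the same composite V_T, each at 0.05, could both claim that role

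*Combined protocol and SAP*

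**What the plan says.** The Endpoints section of the synopsis reads: "The primary endpoint is mGluR5 availability, as measured by FPEB, in cannabis-maintained and abstinent states". Cannabis-maintained and abstinent states both occur only in CUD subjects, so on its face the sentence leans towards the Day 28 against Day 0 comparison.

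The Project Summary leans the other way: "The goal is to test the overall hypothesis that mGluR5 availability is higher in people with CUD compared with HC".

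The background does not settle it. Section 2.2, A.5 gives a central hypothesis that covers both upregulation with chronic use and possible reversal on abstinence. A.7 labels the central hypothesis as belonging to Aim 1. Section 4.2 repeats both.

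Section 9.4.2, where the primary analysis should be defined, contains only a cross-reference to 9.2. There, one composite V_T, the mean over six regions, is "to be used in all PET analyses", and two tests of it are planned:

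- **Aim 1.** ANOVA of CUD against controls, at an alpha of "0.05 (two-tailed test) and two groups (cannabis vs. control". The decision rule is: "A significant group difference suggestive of higher mGluR5 availability in CUD subjects will be considered supportive of Hypothesis 1".
- **Aim 3.** Repeated measures ANOVA within CUD, also at 0.05: "Specifically, models will evaluate: (1) changes in mGluR5 availability" is the first of three models. Support requires a significant result showing lower availability after abstinence.

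Each rule is tied to its own hypothesis. No section links either one to the primary endpoint.

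**The concern.** A primary endpoint should lead to one prespecified decision. Here a significant group difference without an abstinence effect, or the reverse, could be presented afterwards as the primary result, because nothing written in advance says which comparison decides.

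The two comparisons also support different claims. Aim 1 compares non-randomised groups at one time. Aim 3 is a before-after change without a control arm. Which of them is primary determines what the study can say it has shown.

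There is a practical consequence as well. Section 10.1.2 lists the primary endpoint having been met among the possible grounds for suspending or terminating the study, and no section defines what meeting it means.

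**Working it through.** **Inputs**

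- Aim 1 (section 9.2): 30 per group, d = 0.82, two-tailed alpha 0.05, stated power 81.07%.
- Aim 3 (section 9.2): n = 30, d = 0.58, alpha 0.05, stated power 80.13%. Sidedness is not stated; the ANOVA F-test is two-sided. I take d as the mean change divided by the SD of the change. The plan does not say so.
- The Day 0 CUD scans enter both tests (section 6.1.1), so the test statistics are correlated.
- The within-person correlation of V_T between Day 0 and Day 28, ρ, is not in the documents. I assume a range of 0 to 0.95.

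**Step 1: the plan's own power figures**

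- Aim 1: noncentrality d√(n/2) = 0.82 × √15 = 3.18 on 58 df gives 87.8%, against 81.07% stated.
- Aim 3: noncentrality d√n = 0.58 × √30 = 3.18 on 29 df gives 86.7%, against 80.13% stated.

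Neither figure reproduces at alpha 0.05. At two-sided 0.025 the powers are 80.7% and 78.7%, which are close but not equal to the stated values. Other slips fit as well: at 0.05, 25 per group gives 81.1% for Aim 1, and d of about 0.53 gives 80.1% for Aim 3.

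**Step 2: correlation of the two statistics**

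With equal variances σ² and n = 30 in each set of scans, the group difference has variance 2σ²/n, the change has variance 2(1−ρ)σ²/n, and their covariance is (1−ρ)σ²/n. The correlation is therefore √(1−ρ)/2, which is 0.50 at ρ = 0 and 0.11 at ρ = 0.95.

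**Step 3: false-positive rates with both nulls true, each test two-sided at 0.05 (bivariate normal)**

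| ρ | Either test, any direction | Either test, predicted direction | Both tests, any direction |
|---|---|---|---|
| 0 | 9.1% | 4.5% | 0.9% |
| 0.5 | 9.4% | 4.7% | 0.6% |
| 0.8 | 9.6% | 4.8% | 0.4% |
| 0.95 | 9.7% | 4.9% | 0.3% |

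The last column is 5% + 5% minus the first rate. If the tests were independent, the first rate would be 1 − 0.95² = 9.75%. Simulated two-sample and paired t-tests sharing the Day 0 scans gave 9.0% to 9.7% for the first rate. The comparators for a single test are 5% in any direction and 2.5% in the predicted direction.

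**Step 4: what the remedies do**

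- Holm (smaller p against 0.025, then the other against 0.05): with both nulls true, the chance of any rejection is 4.6% to 4.9%. Simulated power at the planned effects, for ρ of 0.5 and 0.8, is about 85.7% for Aim 1 (from 87.8%) and about 84.7% for Aim 3 (from 86.7%).
- Fixed order, Aim 1 first: Aim 1 stays at 87.8%. Aim 3 has 77.9% at ρ = 0.5 and 77.2% at ρ = 0.8.

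**The case against.** The strongest reply is that separately stated aims in a mechanistic, non-randomised imaging study are commonly tested at 0.05 each. The plan has also already removed regional multiplicity by using one composite. That would carry more weight if each aim had its own primary endpoint. Here one endpoint serves both tests, and simply naming one contrast as primary would meet the point without dividing alpha.

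A reader might infer that the primary-endpoint error rate is about 9.5%, so that the nominal 5% fails. The documents do not support that as a flat statement. It requires an either-test rule that appears nowhere in the plan, and it counts wrong-direction results, which both support rules exclude. Each directional rule gives false support at most 2.5% of the time, so the chance of either cannot exceed 5%. What stands is the near-doubling relative to one test if either result may be claimed.

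A reader might also take the stated powers as evidence of a hidden split to 0.025. They match 0.025 only roughly, other slips fit as well, and the written alpha is 0.05 both times.

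Nor should the possibility that the two tests disagree be counted as a harm of this gap. At the planned effects that is mostly ordinary type II error, and neither remedy removes it.

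**Conclusion.** The point holds as an undefined primary contrast, and should be corrected in the plan. The data stay valid, but the primary conclusion is not fixed in advance.

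The error rate depends on a rule that the plan omits: about 9% to 9.7% two-sided if either test suffices, about 4.5% to 4.9% if only predicted-direction results count (2.5% for one test), and under 1% if both are required. These figures assume that both nulls are true, variances are equal and n is 30 throughout. They depend little on the unknown within-person correlation.

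The Project Summary and A.7 favour Aim 1, and the endpoint sentence favours Aim 3. Neither is tied to the primary analysis, so a reader cannot resolve the question from the text.

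**What to change.** In the synopsis Endpoints section and in 9.4.2, name two primary contrasts on the gray-matter-masked composite V_T: CUD against controls at Day 0, and Day 28 against Day 0 within CUD. Test them by Holm at a family alpha of 0.05. This needs a few sentences and no extra participants or scans. The cost is about 2 points of power per test on the recomputed figures, taking d = 0.58 as a paired effect size.

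The simpler alternative is to name CUD against controls as the sole primary contrast, in line with the Project Summary, and the abstinence change as key secondary. Aim 1 then loses nothing. If the secondary is tested only after a significant primary, its power is about 77% to 78%. That is roughly 9 points below the recomputed 86.7%, and also below the stated 80.13%.

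Separately, reconcile alpha, d, n and power in 9.2, since 81.07% and 80.13% do not reproduce at 0.05. Until that is done, the stated powers should not be used to argue that either option has power to spare.

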#### **Study Population**

- (1) Individuals with cannabis use disorder
- (2) Healthy controls

#### **Accrual Ceiling**

Our target enrollment for study completion is 60 subjects: 30 cannabis use disorder (CUD) subjects and 30 healthy controls.

#### **Phase**

N/A

#### **Description of Sites/Facilities Enrolling Participants**

Yale PET Center, Yale MR Center

#### **Description of Study Intervention**

#### **Research Design and Methods:**

#### Research Subjects & Recruitment (Aims 1, 2, and 3)

Subjects: A total of 60 subjects will be recruited: 30 with cannabis use disorder (CUD) and 30 healthy controls (HC) who do not use cannabis. Each HC will be carefully matched to each CUD subject by age, sex, socioeconomic status, education, nicotine use, and other relevant variables. CUD subjects will undergo PET, an optional EEG, and cognitive testing at Day 0 and Day 28. HC will undergo these same measurements at Day 0 only. Some study participants will be also enrolled in HIC # 2000032181 ("SV2A Density Cannabis Use Disorder"), since that study has shared goals and study personnel with our study. We have staff that are common to both studies. If a subject is also enrolled in HIC# 2000032181, common procedures except for PET scanning will be performed once between the two studies (i.e., MRI and cannabis abstinence procedures will not be duplicated). Whichever study the subject first signs up for will be where the abstinence data will be tracked. The subject would sign a release of information to share the information with the other study.

Recruitment and Screening: Subjects will be recruited with clinicians at Yale and in the greater Connecticut community with whom we have a long history of successful collaboration, including long-standing relations with the Yale Psychiatric Hospital inpatient and outpatient services and mental health clinics in the Greater New Haven area, as well as through flyers, public advertisement (newspaper, radio, internet postings), social media, and word of mouth. Subjects will be appropriately compensated for their participation in the study and retained during the cannabis abstinence period using our validated contingency management paradigm.

Study Schedule: Day 0: CUD subjects and healthy controls (HC) undergo PET scanning, an optional EEG, and cognitive testing. Days 1-27: CUD subjects abstain from cannabis use, aided by our validated contingency management strategy. Day 28: CUD subjects who are abstinent from cannabis use undergo repeat PET scanning, an optional EEG, and cognitive testing. Study Procedures: Eligible subjects will undergo an MRI scan for coregistration of PET data and for individualized source analysis of EEG. CUD subjects will be instructed not to use cannabis after midnight of Day 0, and last use of cannabis will be recorded. On Day 0, CUD subjects and HC will be scanned via PET, administered EEGs, and undergo cognitive testing. The same CUD subjects scanned on Day 0 will then be aided with cannabis abstinence and monitored over the next 4 weeks. On a weekly basis between Days 1-27, CUD subjects will be administered (1) the Withdrawal Discomfort score of the Cannabis Withdrawal Checklist, (2) the Cannabis Withdrawal Scale, which has subjective and objective (vital signs, weight) items, (3) Visual Analog Scale for Mood States, and (4) Pittsburgh Sleep Quality Index. CUD subjects will receive motivational enhancement and contingency management (CM) to promote and maintain abstinence. The escalating CM weekly payment schedule for cannabis abstinence is as follows: \$50, \$75, \$125, \$200, \$650 (four-week abstinence bonus). If a participant is already getting paid to abstain from cannabis as part of their participation in another study (i.e. HIC# 2000032181), we will not pay them the usual amount (\$1100) to

abstain for 28 days in our study. Instead, we will pay them a bonus of \$400 which when combined with what they will get paid for abstaining for the other study will amount to more (\$400+1100) than what they would get if they abstained for just one study. If the subject is asked to come in CUD subjects will be required to come to the clinic two days a week for (1) motivational enhancement, (2) escalating contingency management, (3) verbal confirmation of abstinence, (4) urinary drug testing to detect cannabis exposure in the past 1-24 hours, (5) supervised collection of urine samples to assay THC-COOH, the principal metabolite of THC. To account for dilution, urinary THC-COOH: creatinine (T:C) ratio will be calculated. Abstinence will be confirmed if the weekly means of urinary T:C ratio decreases over time and does not increase by more than 50% relative to the prior specimen.[113-115] On Day 28, CUD subjects will undergo a second PET scan, an optional EEG, and cognitive testing. The CUD subjects who relapse between the first and second scans (expected to be 10% of CUD subjects) will be: 1) considered dropouts and 2) referred for treatment if so desired. We will replace dropouts with new CUD subjects to ensure maintenance of adequate statistical power for hypothesis testing. We have accounted for dropouts in the analytic plan, study timeline, and budget. Cannabis Assessments: CUD severity is assessed using DSM-5 criteria.[51] Cannabis withdrawal is assessed by the Cannabis Withdrawal Scale.[116] Cannabis craving is assessed using a 7-point scale. The Marijuana Problems Scale[117] will assess psychosocial impact of cannabis use. Multiple other clinically relevant features of CUD are described in the section below (Cognitive Testing and Behavioral Symptom Assessment). Detailed information on cannabis use patterns will be obtained using a time-line follow back approach: levels of cannabis consumption (estimated number of joints or edibles consumed) will be determined via interview for lifetime, the past six months, three months, one month, and then for the week prior to the test session as has been described previously [12,66,112,118,119]. Participants will be instructed to consider each day of the week and indicate, for an average week, how much they consumed per drug-use occasion for each length of time assessed. Cognitive Testing and Behavioral Symptom Assessment: The BIS/BAS will be used to assess trait impulsiveness and reward responsiveness.[120,121] Urgency, Premeditation (lack of), Perseverance (lack of), Sensation Seeking, Positive Urgency, Impulsive Behavior Scale will assess five impulsive personality traits. The Eriksen flanker task will supplement the assessment of the ability to suppress responses that are inappropriate to a particular context.[122] In addition, the Probabilistic Reward Task (PRT) will be used to provide an objective endophenotypic measure of reward responsiveness. On each of the scan days, CUD and controls subjects will also be administered neuropsychological tests from the CogState Cognitive Battery [123,124], which we previously showed to be sensitive to detecting cognitive deficits in mood disorders[125]: executive control (Groton Maze Learning task, GMLT; Set-Shifting task, SST and Go No-Go, GNG)[126-134] and working memory (One Back task, ONB, and Two Back task, TWB)[135-137]. Further, the battery has been wellvalidated (studies using CogState batteries have been published in over 100 peer-reviewed journals). Most important for the current study, this battery is ideal for within-subject designs (i.e., it was specifically developed for repeated administration with minimal practice or learning effects). Finally, the CogState has been shown to have high test-retest reliability, thorough coverage of cognitive domains, comparable alternative forms, strong internal consistency, is well established in the general population, and has proven tolerability and acceptability. The entire battery takes approximately 30 minutes. For mood assessment, the

Hamilton Depression Rating Scale (HAM-D) and Montgomery-Asberg Depression Rating Scale (MADRS) will be administered by highly trained and reliable raters. These assessments will be administered at screening and at the time of PET scans.

- C.1.d. Receptor Quantification Methods (Aim 1): (1) Magnetic Resonance Imaging Methods: MRI will be performed on a 3-Tesla Siemens Trio MR scanner (Siemens, Erlangen, Germany). A high resolution, 3-dimensional Magnetization Prepared Rapid Acquisition Gradient Echo (MPRAGE) T1-weighted sequence will be used to acquire sagittal images for anatomical determinations and co-registration (TR=1500ms, TE=2.83ms, FOV=256x256mm², matrix=256x 256mm², slice thickness=1.0mm without gap, 160 slices, voxel size 1.0 x 1.0 x 1.0 mm³). The structural MRI data will serve to guide placement of ROIs for PET and for conducting GMM/partial volume correction (PVC) analyses. We will acquire rs-fMRI and DTI at both imaging time points, and these will be examined on an exploratory basis. A member of the research staff will accompany the study participant to the MR scans and stay for the duration of the session.
- (2) Positron Emission Tomography Methods: Data Acquisition: CUD subjects will participate in two [18F]FPEB scans, while controls will participate in one. Given we and others recently showed a diurnal variation in mGluR5 availability, all mGluR5 scan collection will be at the same time of day. [18F]FPEB will be synthesized in the Radiochemistry Laboratory at the Yale PET Center. 79 The HRRT, or a PET/CT, will be used to image subjects. [18F]FPEB will be administered as either a single bolus lasting up to one minute or bolus plus constant infusion lasting up to 2 hours. In either case, [18F]FPEB will be prepared in a single syringe and administered via software-controlled pump to achieve the desired radiotracer administration schedule not to exceed 5mCi. Syringe and lines will be assayed after scanning to correct for residual activity. Subjects are infused outside the scanner for the first 0-90 minutes during the pre-equilibrium period. Then, they will be scanned for 30 minutes in list-mode during the time the radiotracer reaches steady levels in the brain (90-120 minutes). At the beginning or end of each scan, a transmission scan, or low dose CT, will be obtained and used for attenuation correction. The emission list-mode data will then be binned into 5-min frames, and images will be reconstructed, correcting for attenuation, scatter, randoms, deadtime, and motion (using data from the Polaris Vicra using the MOLAR algorithm^89). Pulse and blood pressure will be obtained before, during, and after scanning. Input Function Measurement: Venous concentrations of [18F]FPEB reach equilibrium by 60 minutes post injection. Therefore,  $V_T$  can be determined from the ratio of activity in tissue to that in venous blood samples. Blood samples will be acquired manually before and during the equilibrium period (90-120 minutes). If the individuals from CUD group are also participating in HIC# 2000032181 and already has an has an arterial line placed, blood may be drawn through the arterial line if intravenous access is unobtainable. Radioactivity concentration in whole blood and plasma will be measured using a gamma counter (Wizard 1480; Perkin-Elmer, Waltham, MA, USA). Up to 6 tablespoons of blood will be drawn per PET scan. Highperformance liquid chromatography (HPLC) will be used to establish unmetabolized parent compound levels. The input function is calculated as the product of the interpolated parent fraction and the plasma concentration values. PET Image Analysis: To compute regional values, a summed PET image will be registered to each subject's T1- weighted MR image

using a six-parameter mutual information algorithm (FLIRT, FSL 3.2, Analysis Group, FMRIB, Oxford, UK), which in turn will be registered to an MR template image using nonrigid registration methods (Bioimage Suite, Yale University). Bioimage Suite atlas will be used to identify the primary regions of interest (ROIs) (Fronto-limbic circuit - hippocampus, amygdala, cingulate, dlPFC, vmPFC, and OFC). Outcome Measure Calculation: In humans, there is not a region that is completely devoid of mGluR5 — we and other have shown there is specific binding in the cerebellum.  $^{91,92}$  Therefore, we plan to examine  $V_{\rm T}$   $^{93}$  The  $V_{\rm T}$ images will be spatially normalized to a standard template (MNI, Montreal Neurological Institute) and analyses will be performed to assess ROI differences between groups ROIs. Gray Matter Masking: To partially account for partial volume effects, binary GMM will be employed. Individual MR images will be segmented with FAST (FMRIB's Automated Segmentation Tool, v3.1; The Analysis Group, FMRIB, Oxford, UK) to obtain gray matter (GM), white matter (WM), and cerebrospinal fluid (CSF) masks. The individual GMM images will be used to mask the candidate ROIs to obtain the mean regional values limited to GM voxels. GMM  $V_T$  will be the primary outcome measure. Partial Volume Correction (PVC): We will also examine the effect of full partial volume correction on between-group differences in mGluR5 availability. PVC will be applied to the PET data on a frame-by-frame basis. The MR images will be segmented into GM, WM and CSF using FAST. Masked images will then be blurred by convolving the image with a Gaussian point spread function to achieve the resolution of the PET scanner (~3 mm). GM pixels will be corrected for spill-in and spill-out of activity from WM. Activity in CSF is assumed to be zero and activity in WM is assumed to be uniform and is estimated from each image. 95 This method creates a set of PVC-corrected PET dynamic images, which are then used to create PVC  $V_T$  images. Given the high resolution of the HRRT, we do not expect PVC to produce a substantial change in the data compared to the GMM analysis described above.

